injection and high-risk sex. Current interventions include education, needle and syringe exchange programs, social marketing of condoms, voluntary counseling, and testing, and STI diagnosis and management. Methadone maintenance therapy (MMT) for IDUs started as a pilot program in 2008 in Haiphong and HCMC, two of the highest prevalence provinces for injecting drug use. In HCMC, where 51.8 % of IDUs are HIV positive (HCMC Provincial Aids Committee PAC, 2009), MMT pilot program started in three districts in May 2008 (district 4, 6 and Binh Thanh). On December 2009, 784 patients were under MMT and 235 were receiving ARV. 30% of patients under MMT are HIV+ (HCMC PAC, 2009). A conference held in HCMC on July 2009 concluded positively on the results of the pilot program in terms of 1) Improvement of drug adherence for patients receiving ART; 2) Improvement of social rehabilitation; and, 3) Decrease in drug use (heroin) and risk of HIV transmission. According to interviews conducted and information provided by HCMC health authorities, there are around 15,000 active drug users in the City. Heroin appears to be the main drug used but opium is also widely consumed (mostly among (“old addicts”) and there is a rapid spread of methamphetamine use, frequently through intravenous (IV) route. Consequently, the HIV transmission rate due to needle sharing is high. Between 50% and 70% of drug users are also infected with HCV and an elevated rate of tuberculosis has been reported.

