## **Design**

This is an open-label follow-up study. The project proposes to enroll up to 500 opiate dependent individuals entering Medication Assisted Treatment (Methadone or buprenorphine/naloxone) at Go Vap Clinic, HCMC, Vietnam. All participants who appear to meet inclusion criteria and who express interest in drug treatment will be invited to be screened for participation in the research. The investigators expect that around 40% of them will be also HIV-positive and so will receive appropriate treatment. All participants will receive BDRC sessions (weekly for 12 weeks, monthly thereafter until week 52).

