The analyses will follow the same overall analytic strategy for each set of models. First, the participant characteristics will be examined separately. For a given characteristic, the analyses will first test for heterogeneity (interaction) between the characteristic and the stratifying variables of treatment and HIV status. Two types of heterogeneity are possible: the characteristic could have effects that differ across some combination of the treatment and HIV groups (three-way interaction) or its effects may be independent of one variable but differ across levels of the other (two-way interaction). In either of these cases, stratum-specific estimates of the effects will be reported. If no heterogeneity is detected, the adjusted (pooled) estimates of effect will be reported. In each case, the estimates on an appropriate scale (e.g., odds ratios, or regression coefficients associated with interpretable changes in the level of the participant characteristic), together with appropriate confidence intervals will be reported. Once the univariate effects of the different characteristics will be assessed, multivariate models containing what appear to be the important characteristics will be performed, and these models will be implemented and reported in the same way as for the univariate models.

**Data Analyses for Economic Outcomes (Aim 4):** Standard cost-effectiveness and cost-utility analyses will compare costs and benefits of the two approaches (Gold et al., 1996; Haddix et al., 2003). The analyses will be carried out from a societal perspective which means that all costs and benefits, regardless of who pays or incurs them, will be included.

Benefits may be considered as reductions in sex risk behaviors (e.g., condom use and decreased number of partners) and less risky drug-use practices (e.g., decreased needle sharing and works sharing) during follow-up. In addition, a measure of the quality-adjusted life-years (QALYs) of sex partners saved by the intervention versus the standard of care will be estimated. Benefits will be compared to the direct and indirect costs (i.e., lost productivity) of the intervention and standard of care procedures. Relevant costs include time for the administration of the HIV counseling and testing, HIV test kits, completion of intervention questionnaires, time of staff to collect blood and follow-up assessment data and the time of participants to complete the follow-up assessments.

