Incremental cost-effectiveness ratios will be computed to find the additional net cost (costs minus benefits) per outcome (e.g., cases of HIV transmission prevented or QALY saved) by administering the behavioral intervention over standard procedures. To check the sensitivity of results, univariate and multivariate sensitivity analyses, in which parameter values in the mathematical models are varied from baseline values, will be conducted.

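### The economic analysis adopts a societal perspective but defines QALYs for sex partners only, leaving out the treated participants and their needle-sharing partners

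*Combined protocol and SAP*

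**What the plan says.** All places are in the combined protocol and SAP.

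- **Status.** Under Primary outcome variable(s), cost-effectiveness ratios are the fourth primary outcome.
- **Perspective.** Analysis Plan, Data Analyses for Economic Outcomes (Aim 4), says the analysis is societal, so that "all costs and benefits, regardless of who pays or incurs them, will be included".
- **QALY measure.** The next paragraph says "a measure of the quality-adjusted life-years (QALYs) of sex partners saved by the intervention versus the standard of care will be estimated". No other QALY measure is defined anywhere.
- **Other benefits.** The same paragraph allows benefits to be expressed as reduced sexual risk and as "less risky drug-use practices (e.g., decreased needle sharing and works sharing) during follow-up".
- **Ratio.** The outcome in the incremental ratio is given by example as "cases of HIV transmission prevented or QALY saved", gained "by administering the behavioral intervention over standard procedures". Sensitivity analyses will vary parameter values.
- **Costs.** The costs named as relevant include "time of staff to collect blood and follow-up assessment data and the time of participants to complete the follow-up assessments". Under Study Procedures, the DATCAP instruments separately collect program costs (medication, personnel and facilities among them) and client costs.
- **Population.** Key inclusion criteria require heroin injection in the past 30 days. The Background states that "the HIV transmission rate due to needle sharing is high".

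**The concern.** A perspective that admits every benefit does not fit a QALY measure limited to one group of third parties. The people left out are those the project is built around. The Innovation section rests the work on preventing infection in HIV-negative participants and on effective treatment of those already infected. The Analysis Plan measures HIV incidence and viral load in participants, and the WHOQOL-BREF is collected from them at baseline and months 3, 6, 9 and 12. None of this is linked to the QALY measure. Needle-sharing partners are the other obvious beneficiaries in a population selected for recent injecting.

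At stake is a primary-outcome ratio in a project meant to support expansion of treatment. Followed as written, the cost-utility analysis could omit health gains that its own perspective says must be included. The planned sensitivity analyses would not show this, because they vary parameter values and not whose QALYs are counted.

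A smaller point concerns costs. The follow-up assessments are done by research staff, and a routine program would not carry them. Their cost should be distinguishable from the cost of delivering treatment.

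**Working it through.** The plan states no cost, QALY or ratio for this aim, so there is no figure to reproduce. The check sets the passages side by side and adds simple algebra.

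**1. Whose benefit is counted, and how**

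| Group | Behavioral units | HIV transmissions prevented | QALYs |
|---|---|---|---|
| Sex partners | yes, through sexual risk | possible, route not restricted | yes, named |
| Needle-sharing partners | yes, through needle and works sharing | possible, route not restricted | not named |
| Participants | as reporters of the behavior | possible; incidence is measured | not named |

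The ratio paragraph speaks of QALYs saved without restriction, but it does not replace the definition given just before it.

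**2. Effect of QALY scope**

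Let ΔC be the net incremental cost, held fixed and positive. Let ΔQ(all) be the QALYs gained by sex partners, needle-sharing partners and participants together, and let s = ΔQ(sex partners) / ΔQ(all). Then

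[ΔC / ΔQ(sex partners)] ÷ [ΔC / ΔQ(all)] = 1/s.

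The documents do not give s. Assumed values, for illustration only:

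| s | 0.75 | 0.50 | 0.25 | 0.10 |
|---|---|---|---|---|
| Cost per QALY multiplied by | 1.33 | 2 | 4 | 10 |

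**3. Research follow-up time**

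Inputs: up to 500 participants (Design), and two follow-ups, at 6 and 12 months, of about one hour each (Study Procedures). Participant time is at most 500 × 2 × 1 h = 1,000 h, or 1,000 × 0.9 = 900 h at the anticipated 90% follow-up. Staff hours are not given.

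Let r be the research share of intervention-side incremental cost and q the fraction of the same research cost borne by the comparator. The ratio with research cost, divided by the ratio without it, is [(1 − r) + r(1 − q)] / (1 − r). Both r and q are assumptions:

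| r | q = 0 | q = 0.5 | q = 1 |
|---|---|---|---|
| 5% | 1.05 | 1.03 | 1.00 |
| 10% | 1.11 | 1.06 | 1.00 |
| 20% | 1.25 | 1.13 | 1.00 |

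If both strategies carry the same assessments, the effect is nil.

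**4. Dependence on the comparator**

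The increment is described as the behavioral intervention over standard procedures, yet under Design "All participants will receive BDRC sessions (weekly for 12 weeks, monthly thereafter until week 52". The study therefore contains no group without the counseling, and the sign of ΔC cannot be worked out from the plan.

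**The case against.** The best defense is that the plan never says QALYs are confined to sex partners. It introduces that measure as an addition to the behavioral benefits, lists reduced needle and works sharing among those benefits, and lets the ratio use HIV transmissions prevented by any route. This stands in part: a reader who inferred that needle-related benefit is absent from the economic analysis would be wrong. It does not supply a QALY measure for anyone else, and a benefit left in behavioral units does not enter a cost per QALY.

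Three further inferences are tempting and not supported.

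- *Charging research time contradicts the societal perspective.* It does not. A perspective that admits all costs can include this time. The valid point is only that it is a cost of the study and not of the program.
- *Medication costs are left out because the Aim 4 list does not name them.* The list is introduced as non-exhaustive, and the program DATCAP collects them.
- *The overstatement can be sized, for example at 2- to 5-fold.* Those figures are 1/0.5 and 1/0.2. They need an assumed 20 to 50% sexual share of averted partner infections and a positive net cost. The documents give neither. Net cost is defined there as costs minus benefits and could be negative.

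It is also fair to object that widening the scope is not free. Recruitment encourages participants to bring friends who inject, so some needle-sharing partners may be enrolled and their gains counted twice. The documents describe no utility weights, and present the WHOQOL-BREF only as a four-domain instrument.

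**Conclusion.** The point holds as an internal inconsistency in the QALY scope: all benefits are to be counted, but the only defined QALY measure leaves out participants and needle-sharing partners. It deserves correction because the ratio is a primary outcome.

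Overstatement of cost per QALY by 1/s follows only if net incremental cost is positive and held fixed, and the omitted groups gain QALYs. The size is unknown because s is not given. The direction also depends on the comparator, which is a separate unresolved problem; settling it would not repair the QALY scope.

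The research-time point is a matter of clear reporting. Its effect on the incremental ratio ranges from none upward, according to what the comparator carries.

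**What to change.** In the Aim 4 paragraphs of the Analysis Plan:

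1. Define QALYs gained as those of participants, sex partners and needle-sharing partners. The RAB already records numbers of both kinds of partner.
2. Add an overlap rule so that a partner who is also enrolled is counted once. The RAB as described gives numbers of partners, so the extent of overlap may have to be assumed.
3. State the source of the utility weights and label it as an assumption.
4. Extend the planned sensitivity analyses to vary the QALY scope, the overlap and the utility weights.
5. Report research-only follow-up assessment time separately from program delivery cost, and show its inclusion in a sensitivity analysis.

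The cost is analysis wording and a larger model, using data largely already collected, with no new visits. The downside is more modelling assumptions, chiefly the utility weights and the partner overlap, which must be shown openly.

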### **Study Procedures**

#### **Procedures**

All participants who express interest in participating in the study and consent to participate will receive MAT, BDRC and HIV treatment if needed.

**Methadone Treatment:** The project will implement a standard treatment protocol in accordance with evidence-based practice and Vietnamese policy. As mentioned previously, the program will be co-located in the Go VAP HIV treatment clinic site where care and treatment services for HIV/AIDS patients are provided: consultation, ART dispensation, home-based care, counseling and testing, social services, TB/HIV care, help groups, vocational training (for eligible patients). The site will be staffed with the following clinical professionals: 2 doctors; 2 pharmacists; 2 nurses; and 5 counselors. Importantly the methadone treatment process will incorporate the following features:

- Dosage of methadone will follow the Ministry of Health guidelines
- Treatment will be started with low doses (usually 20-30 mg)
- The dose will be increased slowly (usually 5-10 mg every 3 days) to reduce the risk of overdose
- Most patients not receiving ARVs will be able to be managed on 60 mgs/day

In practice, higher doses are often necessary, particularly in patients on ART. In case of difficulties, doctors in charge seek advice from the city technical working group, with whom regular meetings are held. Clinical consultation will also be available from the Investigative team for this research. Supervision of the prescribing physician will be provided by the on-site PIs and co-investigators, Drs. [name], and [name]. Patients receiving methadone will attend the Go Vap program daily. All oral methadone doses are consumed daily under direct observation by the pharmacist. Random observed urine samples are obtained at least twice per month tested for opiates and other drugs commonly abused in Vietnam.

Methadone will be provided by the Central Procurement Company (Ministry of Health), with strict control from agents from both organizations regarding quality and quantity of the methadone delivered. Monthly reporting of methadone use and request for next month's supply are sent to the Pharmaceutical Department of the HCMC Health Department for control and approval. Used bottles of Methadone are destroyed according to a process approved and controlled by the Environmental and Natural Resources of the city.

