- 2) *Evaluate barriers and facilitators to implementation of integrated MAT/HIV treatment.* For this aim the study will carefully document the “events” or “factors” that are identified as having an influence on the ability and speed of implementation. Three stakeholder groups will be monitored—the drug using and patient population, the program staff, and the local government and non-government organizations. Data will be assembled using a monthly implementation log and formally assessed using semi-structured interview strategies.
- 3) *Evaluate patient retention and medication adherence in integrated MAT/HIV Care.* This aim will be critically important in documenting the success of implementation of the program. The study will carefully monitor through the baseline, 6- and 12-months assessments both retention in treatment and response to treatment. Retention will include measures of medication visit completion for expected methadone and Suboxone® administration visits as well as adherence to antiretroviral medication. Biological markers of these measures will also be collected. Results of monthly urinalyses for all participants will be reported and semiannual viral load measures for HIV positive patient will be summarized.
- 4) *Estimate the costs and benefits of MAT treatment strategies.* A cost-effectiveness analysis is an economic evaluation technique that may be used to evaluate multiple strategies to achieve an outcome. A cost-utility analysis is a special kind of cost-effectiveness analysis that may be used to compare strategies that affect morbidity and mortality (Gold et al. 1996; Haddix et al. 2003). One potential barrier to implementation of an enhanced intervention is the number of resources that must be devoted to administer the additional procedures. However, resource-intensive interventions may be justified through the achievement of better outcomes resulting from administering the enhanced procedures.

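### The only cost-effectiveness ratio that Aim 4 defines needs a comparator that no participant provides and the plan never defines

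*Combined protocol and SAP*

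**What the plan says.** The section Primary outcome variable(s) lists cost-effectiveness ratios as the fourth primary outcome. Aim 4, under Objectives and again in the Analysis Plan, concerns the costs and benefits of MAT strategies.

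The subsection Data Analyses for Economic Outcomes (Aim 4) describes the comparison in three ways:

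- The analyses will "compare costs and benefits of the two approaches".
- QALYs of sex partners "saved by the intervention versus the standard of care will be estimated".
- The ratio itself is an additional net cost (costs less benefits) per outcome, such as an HIV transmission averted or a QALY gained, obtained "by administering the behavioral intervention over standard procedures".

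The Procedures section says that those who consent "will receive MAT, BDRC and HIV treatment if needed". The Design section gives every participant BDRC sessions up to week 52 and describes an open-label follow-up study. Overall objectives places all subjects in an integrated MAT programme that includes counselling.

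**The concern.** An incremental ratio needs cost and effect under two conditions. The plan names the second condition as standard procedures or standard of care, but a single cohort in which everyone receives the full package contains nobody in that condition. Nor does a contrast of counselling against no counselling match an aim about MAT strategies.

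What is at stake is one of the four listed primary outcomes. With the comparator open, it could be chosen after the data are in, and each choice changes both the cost difference and the effect difference. A published ratio could then be read as evidence of value over an alternative that the cohort never observed.

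**Working it through.** The plan states no sample size, precision or other figure for Aim 4, so there is nothing to reproduce. The check is whether the ratio can be estimated.

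**Step 1. Formula.** ICER = (C1 − C0) / (E1 − E0), where C is net cost and E is the outcome. Condition 1 is BDRC with MAT. Condition 0 is standard procedures.

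**Step 2. Who can supply each term.** The maximum sample is 500 (Subjects at Sites Other than Penn). All of them are to receive BDRC and MAT. Condition 1 therefore has up to 500 participants, and condition 0 has 500 − 500 = 0. C0 and E0 have no study data.

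**Step 3. Each wording against the design.**

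| Wording in the Aim 4 economic text | Defined? | Contrast available in the cohort? |
|---|---|---|
| Behavioral intervention against standard procedures | No | No: everyone receives BDRC |
| Intervention against standard of care | No | No: everyone is in the integrated programme |
| Two approaches | No | Only if it means the two medications |

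**Step 4. The medication reading.** The analysis text for Aims 1 and 3 expects 40-50% on one medication and 60-50% on the other:

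- 0.40 × 500 = 200 to 0.50 × 500 = 250 on one
- 0.60 × 500 = 300 to 0.50 × 500 = 250 on the other

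Both groups receive BDRC, so their difference does not estimate the BDRC increment. Assignment follows clinical evaluation. Longer addiction, more prior treatments or a risk of antiretroviral interaction make Suboxone more likely, so a cost or effect difference would be confounded. The Abstract, Innovation, Implementation Research Strategy and the Aim 1 analysis text all say that comparing the two is not the purpose.

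**Step 5. Inputs named and inputs needed.**

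| Term | Named source |
|---|---|
| Programme and participant costs, treated cohort | Program-based and client-based DATCAP |
| Risk behaviors, treated cohort | RAB |
| HIV infection, treated cohort | HIV tests at baseline, 6 and 12 months |
| Costs under the comparator | None |
| Outcomes under the comparator | None |
| HIV-transmission parameters | None |
| QALY inputs for sex partners | None (WHOQOL-BREF measures participants and is not linked to QALYs) |

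**Step 6. The HIV outcome as an example.** The Design section states: "The investigators expect that around 40% of them will be also HIV-positive". At 500 enrolled, (1 − 0.40) × 500 = 300 would be HIV-negative at baseline. All 300 are treated. Retesting gives incidence under the programme, but infections prevented equals infections expected without it minus infections observed with it, and the first term has no source.

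**Step 7. Two smaller points on the numerator.** The listed costs include staff and participant time for follow-up assessments. Under Assessments, that is work done by research staff rather than clinicians or counsellors, so it is a research cost. The formula also subtracts benefits from costs, while the benefits described are behavior changes and QALYs. Only benefits expressed in money can be subtracted.

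**The case against.** **A model can supply the comparator.** Transmissions averted and sex-partner QALYs would need a model in any design, and the plan foresees univariate and multivariate sensitivity analyses. It stands that a modelled increment is legitimate. But models are mentioned only in the sensitivity-analysis sentence, with no comparator, structure or parameter source. Varying inputs around base values that are not stated does not fix the contrast.

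**The two approaches are the two medications.** Aim 4 speaks of strategies in the plural, the background expects thrice-weekly Suboxone to reduce costs, and the Implementation Research Strategy disclaims a comparison of outcomes, not of costs. So the phrase is not unrelated to Aim 4. It still cannot yield the ratio as defined, for the reasons in Step 4.

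**Before against after could serve.** The RAB at baseline covers the preceding six months. But the plan does not call that period standard care, and it plans no pre-programme cost data.

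**Stronger readings that the documents do not support:**

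- A reader might infer that the economic analysis has no input sources. DATCAP, RAB and HIV testing are named for the treated cohort.
- A reader might infer from the short list of relevant costs that medication and counselling are left out. The analysis takes a societal perspective, and DATCAP covers personnel, medications and donated supplies.
- A reader might take the introduction to Aim 4 as a further contrast, since it says "One potential barrier to implementation of an enhanced intervention is the number of resources that must be devoted to administer the additional procedures" and refers to "better outcomes resulting from administering the enhanced procedures". Those sentences give a general rationale for cost-effectiveness analysis and specify no comparison.
- A reader might infer that no ratio is possible. The primary-outcome wording leaves room for other ratios.

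**Conclusion.** The defect holds as a contradiction between the stated ratio and the design. The defined increment cannot be estimated from this study, because 0 of up to 500 participants are under standard procedures and no external or modelled comparator is named. The effect on the ratio's value cannot be calculated, since the documents give no comparator cost or outcome.

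This assumes that the behavioral intervention is BDRC, the counselling that the protocol gives to everyone, and that participants receive what the protocol says. The group sizes in Steps 4 and 6 also assume full enrolment and the expected proportions.

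The text should be corrected before analysis. It ranks below a critical fault: no treatment, safety or retention analysis depends on it, and the repair is to wording, not design.

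**What to change.** Reconcile the Aim 4 economic text with Aim 4 as stated under Objectives:

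1. Remove the behavioral intervention against standard procedures as a contrast estimated from study data. Define or delete the two other wordings.
2. Report primary outcome 4 as a descriptive, average cost per outcome of the integrated programme. Use DATCAP programme and client costs as planned, which on the client side means costs while in treatment. Divide by outcomes already collected, such as the number retained at 12 months.
3. Show before-after RAB changes beside the costs, labelled as uncontrolled. Treat results by medication as descriptive.
4. Keep an incremental, HIV-transmission or QALY ratio only if it is labelled as modelled and the investigators name its comparator and the sources of its cost, effect and QALY inputs before analysis. Otherwise delete it.
5. Exclude research-only follow-up assessment time from programme cost, and subtract only monetised benefits from costs.

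**Cost.** This is a text change that uses data already planned. Two rules must be written: how shared clinic costs are allocated between medications, since both are given in one center, and how costs collected in Year three apply to participants treated in other years. The downside is that study data alone will not show value over an alternative.

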#### **Primary outcome variable(s)**

1) Qualitative assessment: acceptability, barriers, and facilitators to implement medication-assisted treatment for opiate addiction within an HIV-treatment setting; 2) Treatment retention at 6 and 12-month follow-ups; 3) Treatment adherence: Methadone, Suboxone®, HIV treatment, counseling sessions; 4) Cost-effectiveness ratios calculated at the end of the study

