**Data Analyses for treatment and outcomes (Aims 1 and 3):** The sample of up to 500 participants will be split between HIV+ and HIV- participants. The participants will not be assigned at random to Suboxone® or methadone. The assignments will be based on clinical evaluation, and participants with a longer history of addiction, or with higher numbers of previous treatments, or participants who may be at risk for interactions between methadone and antiretroviral medications, will be more likely to receive Suboxone®. The investigators anticipate having about 40-50% of the sample receiving one medication, and 60-50% receiving the other, so there should be adequate numbers for analyses in each treatment stratum.

The goal of the analyses for Aims 1) and 3) is to assess the influences of participant characteristics on treatment outcome, and to examine whether characteristics of good outcome differ across treatment and HIV groups. Thus, the analyses will regard treatment (SUB or METH) and HIV status (+ve or -ve) as strata. Participant characteristics, drawn from the baseline administrations of the Study Specific Questionnaire, ASI, RAB, and ICD-10 assessments, will be the explanatory variables of interest, while binary factors for treatment group and for HIV status will form four strata.

The outcomes of interest include: (1) the durations of time in treatment, and time to relapse to drug use, which will be addressed using Cox proportional hazards models and its extensions; (2) measures of psychopathology and drug or sex risk behaviors, drawn from the ASI and the RAB at the 6 and 12 month points, which will be analyzed using linear or nonlinear (e.g. logistic or ordinal) mixed effects models; (3) self-reported drug use drawn from the ASI, and monthly UDS tests, which will also be analyzed using linear or nonlinear mixed effects models; (4) overall incidence of HIV among those participants negative for HIV at baseline, which will be analyzed using a logistic regression model.

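### Cost-effectiveness ratios are a primary outcome, but nothing ties their planned sensitivity ranges to the sampling error in participants' own outcomes and costs

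*Combined protocol and SAP*

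**What the plan says.** Under Primary outcome variable(s), item 4 is "Cost-effectiveness ratios calculated at the end of the study".

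The method is in the Analysis Plan, in the part headed Data Analyses for Economic Outcomes (Aim 4). Cost-effectiveness and cost-utility analyses "will compare costs and benefits of the two approaches", from a societal perspective. The incremental ratio is the "additional net cost (costs minus benefits) per outcome (e.g., cases of HIV transmission prevented or QALY saved"), gained "by administering the behavioral intervention over standard procedures". Robustness is to be checked by "univariate and multivariate sensitivity analyses, in which parameter values in the mathematical models are varied from baseline values". That is the only uncertainty step stated for Aim 4. The text names no confidence interval, bootstrap, input distribution, net benefit or acceptability curve, and it sets no parameter ranges.

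The same Analysis Plan does promise intervals elsewhere: estimates "together with appropriate confidence intervals will be reported". That sentence comes before the Aim 4 heading and belongs to the participant-characteristic models of Aims 1 and 3.

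**The concern.** Some inputs to the ratio will be estimated from participants: changes in risk behaviour, quality of life, and the costs that participants themselves incur. Those estimates have sampling error. Varying a parameter around its base value shows how much the ratio depends on that parameter. It shows what the data support only if the size of the variation comes from the parameter's standard error, and the plan does not require this.

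A ratio is especially exposed, because its meaning changes when the denominator changes sign. A positive ratio with moderate ranges can be read as a settled cost per unit gained when the study cannot tell a small gain from a small loss. A reader of this primary outcome would have no means of telling the two situations apart.

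**Working it through.** The documents state no effect size, SD, HIV incidence, cost figure or target precision, so there is no figure to reproduce. What follows uses the documents' sample sizes with **assumed** effects.

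**Inputs from the documents**
- Total sample: "The sample of up to 500 participants will be split between HIV+ and HIV- participants", so N = 500 at most (Analysis Plan, Aims 1 and 3).
- Medication split: 40–50% against 60–50% (same section), so 200/300 to 250/250.
- Follow-up at 12 months: 90% anticipated (Study Retention), so 180/270 to 225/225 evaluable.

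**1. Precision of a difference, if the two approaches are the two medications**

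SE in SD units = √(1/n₁ + 1/n₂).
- 180/270: √(1/180 + 1/270) = 0.0962, and 1.96 × 0.0962 = 0.189 SD.
- 225/225: √(2/225) = 0.0943, and 1.96 × 0.0943 = 0.185 SD.

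An observed difference in effect or cost below about 0.19 SD therefore has a 95% interval that includes zero.

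**2. Parameter variation against resampling, same assumed data**

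Assume that effect and cost differences are each observed at 0.10 SD, with 180/270 followed and cost and effect uncorrelated.
- Varying each difference by ±50% (an assumed range) moves each from 0.05 to 0.15. The ratio runs from 0.05/0.15 = 0.33 to 0.15/0.05 = 3.0 times its base value, and is always positive.
- A 10,000-draw bootstrap by participant on constructed data gives 95% intervals of −0.09 to 0.29 SD for both effect and cost. The draws divide as follows:

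| | Dearer | Cheaper |
|---|---|---|
| More effective | 72.7% | 12.7% |
| Less effective | 12.5% | 2.1% |

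The effect is negative in 12.5 + 2.1 = 14.6% of draws. The ±50% ranges show none of this.

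This step varies the differences themselves. If group-level inputs were varied instead, a sign change might or might not appear, depending on the ranges, which the plan leaves open.

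**3. When it stops mattering**

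With both differences at 0.20 SD, a normal simulation puts 96% of draws in the more-effective, dearer quadrant. The sign is then nearly settled.

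**4. If the comparator is modelled standard care**

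Only the enrolled side can be resampled. With 500 × 0.90 = 450 followed, a mean has a 95% half-width of 1.96/√450 = 0.092 SD, before any uncertainty in the comparator inputs.

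**5. If, and only if, infections averted were counted from observed seroconversions**

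Assume 300 HIV-negative participants for one year (60% of 500, before loss to follow-up; 270 after it), 6 infections observed, and 12 expected without the programme, held fixed. The exact Poisson limits for 6 are 2.2 to 13.1. Infections averted are 12 − 6 = 6, with limits 12 − 13.1 = −1.1 to 12 − 2.2 = 9.8. Varying the 6 by ±50% (3 to 9) gives 3 to 9 averted, always positive. With 9 observed against 18 expected, the limits are 0.9 to 13.9 and the sign is fixed.

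**The case against.** Several points on the other side have force.

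- **The text does not exclude sampling error.** It sets no ranges, so they could be taken from confidence limits, and a multivariate analysis could be run probabilistically. The plan also refers to standard methods in two texts that are not available here. A reader might infer that the ratio will carry no sampling error, or that its ranges are arbitrary. The documents do not say so. They only fail to require the link.
- **Parameter variation can show a sign change.** Step 5 is itself a one-way variation: moving observed infections across their exact limits takes the denominator through zero. The gap lies in how ranges are chosen, not in what the method can do.
- **The HIV example may not apply.** A reader might infer that the denominator rests on a handful of observed infections. The documents do not say that participants' seroconversions feed the ratio. HIV incidence is analysed under Aims 1 and 3. The Aim 4 text lists reductions in risk behaviour and QALYs of sex partners as benefits, and refers to mathematical models. Transmissions prevented may well be modelled from behaviour change.
- **The comparator is unsettled.** The ratio contrasts counselling with standard procedures, yet the Design section says "All participants will receive BDRC sessions (weekly for 12 weeks, monthly thereafter until week 52"). The two approaches are not defined either, and the Implementation Research Strategy disclaims a direct comparison of outcomes between the medications. With standard care as comparator, its inputs come from outside the study. With 6 infections observed, assumed counterfactuals of 6, 12 and 18 give 0, 6 and 12 averted, a spread similar to the sampling range. Varying the comparator inputs remains the right tool for that part.
- **This is a non-randomised feasibility study with no stated threshold or decision rule for the ratio.** That lowers the priority.

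These points limit the claim without removing it. Whatever comparator is chosen, the study-derived inputs have sampling error, and the stated method does not require it to be carried into a primary outcome.

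**Conclusion.** The concern holds in a limited form. The ratio is a primary outcome, its only stated uncertainty step is variation of parameters from base values, and nothing ties that variation to the sampling error of participants' outcomes and costs.

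The consequence depends on the size of the effect. At the planned sample size, differences below about 0.19 SD between the medication groups leave the sign open, and ±50% ranges around a positive difference would not show it. At 0.20 SD in both cost and effect the sign is nearly fixed. These figures rest on assumed effects, on reading the two approaches as the two medications, and on an assumed ±50% range. The HIV figures are conditional on a denominator that the documents do not specify.

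The documents do not support saying that the planned ratio must be misleading, or that the data cannot fix its sign. This is a cheap improvement to the analysis text, to be made after the comparator is defined.

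**What to change.** Define the comparator first. Then amend the last paragraph of the Aim 4 analysis as follows:

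1. Bootstrap study-derived inputs by participant, keeping each person's outcomes together with their own client-based DATCAP costs where these were collected.
2. In the same loop, draw external and comparator inputs from stated distributions with a cited source.
3. Report incremental cost and incremental effect separately, each with a 95% interval, together with net benefit over a range of thresholds or a cost-effectiveness plane. An interval on the ratio itself is not interpretable when draws cross quadrants.
4. Keep the one-way analyses, including variation of the comparator inputs, as a supplement, and state how each range was set.
5. State that the intervals do not cover confounding from non-random choice of medication, nor between-site variation in programme costs, which come from one clinic.

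The cost is plan wording, analyst time, and the work of specifying and sourcing the distributions. No new data are needed. Because cost data are collected in Year three, paired participant costs may exist for only part of the sample, so the number available should be reported. The ratio will look less precise than under the present text.
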